3.8.3. Other Assessments

- Change from baseline in IWQOL-Lite scales (total score, physical function, self-esteem, sexual life, public distress, and work) by visit
- Change from baseline in EQ-5D-5L index value and VAS score by visit
- Cigarette use

The IWQOL-Lite scale is a 31-item self-report measure of obesity-specific quality of life. IWQOL-Lite provides an overall total score as well as scores on five domains: (1) physical function, (2) self-esteem, (3) sexual life, (4) public distress, and (5) work. The raw scores will be transformed as follows (Tessier et al, 2012)³: the transformed scores range from 0 to 100, with 100 representing the best, and 0 representing the most impaired quality of life.

$$\text{Transformed Score} = \frac{\text{maximum theoretical score} - \text{actual score}}{\text{test score range}} \times 100$$

The EQ-5D-5L is a validated quality of life questionnaire developed by the EuroQol Group in order to provide a simple, generic utility measure for characterizing current health states of patients. EQ-5D-5L is designed for self-completion by subjects. It consists of 2 parts – the EQ-5D-5L descriptive system and the visual analogue scale (VAS).

The EQ-5D-5L descriptive system comprises 5 dimensions: mobility, self-care, usual activities, pain/discomfort, and anxiety/depression. Each dimension has 5 levels.

The 5 dimensional 5-level systems are converted into an index value. Values for theoretically possible health states are calculated using a regression model and weighted according to the social preferences of the U.S. population (Van Hout et al, 2012)⁴. The VAS records the respondent's self-rated health on a vertical visual analogue scale. The VAS has 100 (Best health you can imagine) at the top, and 0 (Worst health you can imagine) at the bottom. This information can be used as a quantitative measure of health outcomes as judged by the individual respondents. EQ-5D-5L self-reported VAS data generates information on the self-perceived overall health-related quality of life. Change from baseline in EQ-5D-5L index value and VAS score will be analyzed.

Number of cigarettes used will be summarized at each visit by treatment sequence and overall.

3.8.3.1. Examination of Subgroups

Subgroup analysis by region (US vs non-US) will be performed for selected endpoints, including but not limited to, change from baseline in PANSS total and subscale scores, and PANSS response.

3.8.4. Multiple Comparison / Multiplicity

Not applicable.

3.9. Safety Analysis

All safety endpoints will be summarized by treatment sequence and overall for the Safety Population.

3.9.1. Adverse Events

Incidence of treatment emergent AEs will be analyzed as a safety endpoint. Adverse events will be coded by System Organ Class and Preferred Term using the Medical Dictionary for Regulatory Activities (MedDRA[®]) Version 19.0 or higher. The verbatim term will be included in the AE listings.

An AE (coded by preferred term) will be considered as treatment emergent AE (TEAE) if the event is newly occurring or worsening on or after the date of first dose of study drug in this study.

The number and percentage of subjects reporting TEAEs during the treatment period will be presented by treatment sequence and overall for the following categories:

- System organ class and preferred term
- Preferred term, and including the following subset:
 - TEAEs experienced by $\geq 5\%$ of subjects (in any group) System organ class, preferred term, and severity
 - System organ class, preferred term for serious TEAEs
 - System organ class, preferred term, and relationship
 - System organ class, preferred term for study drug related TEAEs
 - System organ class, preferred term, and severity for study drug related TEAEs

If the same preferred term occurred more than once for the same subject, the subject will be counted only once for that preferred term using the most severe and most related occurrence for the summarization by severity and by relationship to the study drug.

In addition, the number and percentage of subjects reporting AEs during the safety follow-up period will be tabulated by the system organ class, preferred term and treatment sequence and overall.

The number and percentage of subjects who have serious adverse events (SAE) and AEs leading to premature discontinuation from the treatment will be summarized by system organ class, preferred term, and treatment sequence and overall.

3.9.1.1. Other significant AEs

In addition, incidence of a selected subset of relevant AEs in this class of drugs (eg, Extrapyramidal symptoms (EPS) TEAEs, AEs associated with abuse potential, drug withdrawal, and suicide related events, etc.) will be summarized by preferred term and treatment sequence and overall. The selection of AEs per subset will be based on the preferred terms and customized or Standardized MedDRA queries (SMQs).

3.9.2. Clinical Laboratory Parameters

Laboratory parameters will be presented in conventional (ie, US) units. Only scheduled laboratory parameters will be included in the summaries, unless specified otherwise. All laboratory data, including those collected at unscheduled visits, will be included in the listings.

Laboratory results including baseline and change from baseline for the Safety Population during the treatment period for chemistry and hematology parameters will be summarized by treatment sequence, overall, and by visit.

Clinical laboratory test values, scheduled or unscheduled, will be considered potentially clinically significant (PCS) if they meet PCS criteria listed in [Table 1](#). The number and percentage of subjects who have postbaseline PCS clinical laboratory values will be summarized by treatment sequence and overall. The percentages will be calculated based on the number of subjects with non-PCS baseline value and have at least 1 postbaseline assessment. All PCS values including baseline PCS values will be included in supportive listings.

Shift tables for selected metabolic parameters (glucose, total cholesterol, LDL, HDL, tryglyceride, and HbA1c) and liver function tests will be presented. The criteria are summarized in [Table 2](#), [Table 3](#) and [Table 4](#).

Table 1: Criteria of Potentially Clinically Significant (PCS) Abnormality for Selected Analytes

Parameters	Criteria
Chemistry	
Albumin	<2.5 g/dL
Alkaline Phosphatase (U/L)	$\geq 3 \times \text{ULN}$
Alanine Aminotransferase (U/L)	$\geq 3 \times \text{ULN}$
Aspartate Aminotransferase (U/L)	$\geq 3 \times \text{ULN}$
Bilirubin, Total	$\geq 2.0 \text{ mg/dL}$
Blood Urea Nitrogen	$>30 \text{ mg/dL}$
Cholesterol, Random	$>300 \text{ mg/dL}$
Cholesterol, Fasting	$\geq 240 \text{ mg/dL}$
Cholesterol, HDL Fasting	$\leq 30 \text{ mg/dL}$
Cholesterol, LDL Fasting	$\geq 160 \text{ mg/dL}$
Creatine Kinase (U/L)	$\geq 3 \times \text{ULN}$
Creatinine	$\geq 2.0 \text{ mg/dL}$
Glucose, Random	$<50 \text{ mg/dL}$ or $\geq 200 \text{ mg/dL}$
Glucose, Fasting	$<50 \text{ mg/dL}$ or $\geq 126 \text{ mg/dL}$
Potassium	$<3 \text{ mmol/L}$ or $>5.5 \text{ mmol/L}$
Lactate Dehydrogenase (U/L)	$>3 \times \text{ULN}$
Prolactin (Female)	$>30 \text{ ng/mL}$
Prolactin (Male)	$>20 \text{ ng/mL}$
Sodium	$<130 \text{ mmol/L}$ or $>150 \text{ mmol/L}$
Triglycerides, Fasting (Female)	$\geq 120 \text{ mg/dL}$
Triglycerides, Fasting (Male)	$\geq 160 \text{ mg/dL}$

Table 1: Criteria of Potentially Clinically Significant (PCS) Abnormality for Selected Analytes (Continued)

Parameters	Criteria
Hematology	
Eosinophils	$>1.0 \times 10^3/\mu\text{L}$
Hematocrit (Female)	$\leq 32\%$
Hematocrit (Male)	$\leq 37\%$
Neutrophils, Absolute	$<1.5 \times 10^3/\mu\text{L}$
Platelets	$<75.0 \times 10^3 \text{ cells}/\mu\text{L}$ or $\geq 700.0 \times 10^3 \text{ cells}/\mu\text{L}$
Leukocytes	$\leq 2.8 \times 10^3/\mu\text{L}$ or $\geq 16.0 \times 10^3/\mu\text{L}$

Table 2: Shifts Category from Baseline to Any Postbaseline for Selected Lipid Parameters

Total cholesterol (fasting) mg/dL
Normal (<200) to High (≥ 240)
Borderline (≥ 200 and < 240) to High (≥ 240)
Normal/Borderline (<240) to High (≥ 240)
Normal (<200) to borderline/High (≥ 200)
Increase ≥ 40 mg/dL
LDL Cholesterol (fasting) mg/dL
Normal (<100) to high (≥ 160)
Borderline (≥ 100 and <160) to high (≥ 160)
Normal/borderline (<160) to high (≥ 160)
Normal (<100) to borderline/high (≥ 100)
Increase ≥ 30 mg/dL
HDL Cholesterol (fasting) mg/dL
Normal (≥ 40) to low (<40)
Decrease ≥ 20 mg/dL
Triglycerides (fasting) mg/dL

Normal (<150) to high (≥200)
Normal (<150) to very high (≥500)
Borderline (≥150 and <200) to high (≥200)
Borderline (≥150 and <200) to very high (≥500)
Normal/borderline (<200) to high (≥200)
Normal/borderline (<200) to very high (≥500)
Normal (<150) to borderline/high/very high (≥150)
Increase ≥50 mg/dL

Table 3: Shift Category from Baseline to Any Postbaseline in Glucose and HbA1c

Serum glucose (fasting) mg/dL
Normal (<100) to High (≥126)
Impaired (≥100 and <126) to High (≥126)
Normal/Impaired (<126) to High (≥126)
Increase ≥10 mg/dL
HbA1c %
Shift from baseline (<5.7%) to postbaseline ≥5.7%
Shift from baseline (<5.7%) to postbaseline ≥5.7% and <6.5%
Shift from baseline (<5.7%) to postbaseline ≥6.5%

Table 4: Shift Category from Baseline to Any Postbaseline in Liver Function Test

Alanine Aminotransferase (ALT) (U/L)
Shift from Normal to ≥3 x ULN
Shift from Normal to ≥5 x ULN
Shift from Normal to ≥10 x ULN
Aspartate Aminotransferase (AST) (U/L)
Shift from Normal to ≥3 x ULN
Shift from Normal to ≥5 x ULN
Shift from Normal to ≥10 x ULN
Bilirubin, Total (mg/dL)

Shift from Normal to >1 x ULN
Shift from Normal to ≥ 2 x ULN

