8.3.10.2. Hematology, Biochemistry, and Urinalysis

Fasting blood and urine samples will be collected at the timepoints specified in Table 3 for specific hematology, biochemistry, and urinalysis assessments listed in Table 4. Subjects will be instructed not to eat or drink anything (except water) for 8 hours before each visit where blood samples for biochemistry and hematology assessments will be collected. Samples will be collected in accordance with the site's standard procedures and analyzed by a central laboratory. Laboratory assessments may be repeated at the Investigator's discretion.

Hematology	Biochemistry	Urinalysis
Hematocrit	General Chemistry	Bilirubin
Hemoglobin	Albumin	Color and appearance
Platelet count	Bicarbonate	Glucose
Red blood cell count	Calcium	Ketones
Total and differential	Chloride	Leukocytes
(absolute) white blood cell	Creatine phosphokinase	Nitrite
count	Glucose	Occult blood
	Lactic dehydrogenase	pH
	Potassium	Protein
	Sodium	Specific gravity
	Total protein	Urobilinogen
	Uric acid	Cotinine
	Endocrine Function Test	
	HbA1c	Microscopic examination of
	Prolactin	sediment, only if urinalysis
	Insulin	dipstick results are abnormal
	Liver Function Tests	
	Alanine aminotransferase	
	Alkaline phosphatase	
	Aspartate aminotransferase	
	Gamma-glutamyl transferase	
	Total bilirubin	
	Renal Function Tests	
	Blood urea nitrogen	
	Creatinine	
	Lipid Panel	
	High-density lipoprotein	
	Low-density lipoprotein	
	Total cholesterol	
	Triglycerides	

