7. GENERAL STATISTICAL METHODOLOGY

In general, summary statistics (n, mean, SD, median, minimum, and maximum for continuous variables, and number and percentage of subjects in each category for categorical variables) will be provided by treatment sequence. All summary tables will be based on observed data, and missing values will not be imputed, unless otherwise indicated. Measurements collected from unscheduled visits or repeated assessments will not be included in the by-visit summary tables or figures, but will be included in the analyses for the PCS postbaseline values, and subject listings. Source data for the summary tables will be presented as subject data listings.

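### SAP 3.9.2 does not extend its exception for unscheduled laboratory values to the any-postbaseline shift tables, so on its default reading Tables 2–4 omit them, including at severity grades that no PCS row covers

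*SAP*

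**What the plan says.** SAP 3.9.2 gives the general rule for laboratory data: "Only scheduled laboratory parameters will be included in the summaries, unless specified otherwise". The rule covers summaries as such, not only by-visit ones. Unscheduled results go into the listings.

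The same section then makes one tabular exception: "Clinical laboratory test values, scheduled or unscheduled, will be considered potentially clinically significant (PCS) if they meet PCS criteria listed in" Table 1. The next paragraph introduces the "Shift tables for selected metabolic parameters" and the liver tests, and does not say which draws feed them. The tables are titled, for example, "Shifts Category from Baseline to Any Postbaseline for Selected Lipid Parameters" (Table 2) and "Shift Category from Baseline to Any Postbaseline in Liver Function Test" (Table 4).

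SAP 7 says that unscheduled and repeat measurements "will not be included in the by-visit summary tables or figures, but will be included in the analyses for the PCS postbaseline values", and also go into listings. Shift tables are named on neither side. SAP 6.1 excludes unscheduled visits from by-visit statistics and keeps one value per scheduled visit.

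Protocol 8.3.10.2 makes off-schedule values possible: "Laboratory assessments may be repeated at the Investigator's discretion". Protocol Table 3 schedules postbaseline laboratory samples at Weeks 4, 12, 24, 36 and 52, the last column also serving as the early termination (ET) visit.

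**The concern.** Tables 2–4 are subject-level worst-case counts. The usual reason for dropping unscheduled draws is to keep by-visit means on a common schedule, and that reason does not apply to them. Unscheduled and repeat draws tend to be taken because something looks wrong, so leaving them out can only lower a worst-case count.

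Two things are at stake in a study whose only objective is long-term safety and tolerability. First, some severity grades appear in the shift tables and nowhere else. An unscheduled ALT of 6 times ULN would count as PCS (3 times ULN or more) but would be absent from the row for 5 times ULN. Second, some thresholds appear in both sets of tables. With different data filters, one report could show two different counts for the same cut-off and give no reason.

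**Working it through.** The plan states no figure to reproduce. The check has three parts.

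**1. Which rule reaches Tables 2–4**

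- For exclusion: the default in 3.9.2 is not limited to by-visit summaries. The only tabular exception in 3.9.2 and SAP 7 is PCS. SAP 6.1 keeps one value per scheduled visit.
- For inclusion: the titles refer to any postbaseline value. The exclusions of unscheduled data in SAP 6.1 and 7 are worded for by-visit output, which these tables are not.

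The default favours exclusion, but no sentence states it for the shift tables.

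**2. Which categories would lose a graded count**

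PCS counts include unscheduled values, so a shift category is exposed only where PCS Table 1 has no equivalent cut.

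| Analyte | Severe shift category (Tables 2–4) | PCS cut (Table 1) | Equivalent PCS count? |
|---|---|---|---|
| ALT, AST | ≥5 and ≥10 × ULN | ≥3 × ULN | No |
| Triglycerides | ≥500 mg/dL | ≥120 (female), ≥160 (male) | No |
| HbA1c, from baseline <5.7% | ≥5.7%, ≥6.5% | no row | No |
| Total cholesterol, fasting | ≥240 mg/dL | ≥240 | Yes |
| LDL, fasting | ≥160 mg/dL | ≥160 | Yes |
| Glucose, fasting | ≥126 mg/dL | ≥126 (high side) | Yes |
| HDL, fasting | <40 mg/dL | ≤30 | PCS is more extreme |
| Total bilirubin | ≥2 × ULN | ≥2.0 mg/dL | Not comparable; ULN not given |

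The absolute-change rows and lower lipid categories in Tables 2–3 also lack a matching PCS cut, but they are not the severe grades.

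The ≥3 × ULN row for ALT/AST shares its threshold with PCS. Those two counts can also differ for another reason: the shift starts from normal, while PCS starts from any non-PCS baseline.

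**3. Size, as illustration only**

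*How often scheduled draws miss a transient excursion.* Assume onset uniform over 52 weeks and a duration of d weeks. A draw at week x sees the excursion if onset lies in [x − d, x]. The share seen is the length of the union of these intervals within 0–52, divided by 52.

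- d = 2: (2+2+2+2+2)/52 = 10/52 = 19% seen, 81% missed
- d = 4: (4+4+4+4+4)/52 = 20/52 = 38% seen, 62% missed
- d = 8: (4+8+8+8+8)/52 = 36/52 = 69% seen, 31% missed
- d = 12: weeks 0–36 and 40–52, so 48/52 = 92% seen, 8% missed
- d = 16: 52/52 = 100% seen

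*What one subject does to a rare row.* The exact (Clopper–Pearson) one-sided 95% upper bound for k of N is the 0.95 quantile of Beta(k+1, N−k). N = 390 is the planned enrolment. The smaller N and the event counts are assumptions.

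| N | k = 0 | k = 1 |
|---|---|---|
| 390 | 0.77% | 1.21% |
| 250 | 1.19% | 1.88% |
| 130 | 2.28% | 3.60% |

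At N = 390 the observed rate moves from 0 to 1/390 = 0.26%.

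**The case against.** The strongest reply is that the SAP never says the shift tables exclude unscheduled values. A reader might infer an express exclusion, and so an under-count fixed by rule. The text does not go that far. The titles can be taken as the specification to the contrary that 3.9.2 allows, SAP 6.1 and 7 restrict only by-visit output, and the mock tables and programming specifications are separate documents not available here. This stands, and makes the omission the default reading only. It does not remove the need for a sentence, because the titles and the section's own rule point in opposite directions.

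A reader might also infer that severe values are lost across all the lipid, glucose, HbA1c and liver tables. They are not. High total cholesterol, LDL and fasting glucose reach the PCS table at the same cut, and low HDL at a more extreme one, with unscheduled values included. For these only the split by baseline category is affected.

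Nor does an unscheduled HbA1c of 6.5% or more vanish. Protocol 7.3 makes it a ground for discontinuation, so the subject appears in disposition. The ET visit includes a laboratory draw, which can recapture the value if the subject attends and it persists. Values judged clinically significant become adverse events (Protocol 13.1), and everything is listed. These routes are real, but only the ET draw can feed the graded count, and it is not assured.

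Finally, the percentages for missed excursions do not measure the loss. They depend on assumed onset and duration and ignore the ET draw. They also say nothing of how often blood is drawn off schedule. A repeat that confirms an abnormal scheduled value adds no subject if that value already met the category.

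**Conclusion.** The point holds as an unresolved inconsistency whose default reading biases worst-case counts downward. It bears mainly on ALT/AST at 5 and 10 times ULN, triglycerides at 500 mg/dL, and HbA1c at 5.7% and 6.5%. It also leaves room for conflicting counts at the thresholds that PCS and the shift tables share.

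The number of subjects affected cannot be derived from the documents. The 81%, 62% and 31% missed at 2, 4 and 8 weeks, falling to 8% at 12 weeks, illustrate the spacing of draws under assumed uniform onset. They suit short-lived enzyme rises better than slow-moving HbA1c. They should not be read as the share of events absent from the tables. The likely effect is a few subjects at most in any row, but in rows expected to be nearly empty one subject is visible. No value is lost from the listings.

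**What to change.** Add to SAP 3.9.2 that the subject-level shift counts in Tables 2, 3 and 4 use all postbaseline values from the treatment period, whether scheduled, unscheduled or repeat, as the PCS analysis does. Restrict this to fasting samples wherever the criterion is a fasting one. Without that condition, non-fasting glucose or lipid results could enter rows defined as fasting. Align SAP 7 by naming the shift tables beside the PCS analyses, and leave by-visit summaries on scheduled values.

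The cost is one SAP sentence with a matching edit in SAP 7, one changed data filter, and possibly slightly higher counts in some rows. If the sponsor does intend scheduled draws only, the SAP should say so and retitle the tables.

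### SAP Table 1 sets the fasting triglyceride PCS limits below Table 2's High boundary, and for women inside Table 2's Normal band

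*SAP*

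**What the plan says.** All the relevant text is in SAP 3.9.2.

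- **Table 1 (PCS criteria).** The row "Triglycerides, Fasting (Female") has a limit of 120 mg/dL or more. The matching row for men has 160 mg/dL or more.
- **Table 2 (lipid shift categories).** The triglyceride bands are not split by sex. The rows "Normal (<150) to high (≥200") and "Borderline (≥150 and <200) to high (≥200") fix Normal as below 150, Borderline as 150 to under 200, and High as 200 or more. Very high starts at 500.
- **Denominator for laboratory PCS percentages.** "The percentages will be calculated based on the number of subjects with non-PCS baseline value and have at least 1 postbaseline assessment".

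The SAP gives no reason for the two triglyceride limits and no baseline triglyceride distribution.

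**The concern.** The two tables classify the same fasting sample in opposite ways, and the denominator rule carries the conflict into a reported percentage in two directions.

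- **Small changes are counted.** A woman who moves from 119 to 121 mg/dL becomes a new PCS case while staying Normal in Table 2.
- **Larger changes can be missed in this table.** A woman at 130 mg/dL at baseline is Normal in Table 2 but already PCS in Table 1. She is outside the PCS at-risk set whatever happens later.

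The primary objective is long-term safety, and the protocol's introduction presents the product as a way to reduce weight gain and the metabolic problems that go with it. Triglycerides are one of the laboratory results a reader will look at first. Their PCS percentage would not mean the same as the PCS percentages for total cholesterol, LDL and glucose beside it.

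**Working it through.** There is no stated figure to reproduce. The check compares the two tables, then illustrates the denominator effect.

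**Step 1. PCS limits against shift bands (SAP Tables 1, 2 and 3; mg/dL, fasting)**

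| Analyte | PCS limit (Table 1) | Abnormal category (Tables 2 and 3) | Relation |
|---|---|---|---|
| Total cholesterol | ≥240 | "Normal/Borderline (<240) to High (≥ 240") | equal |
| LDL | ≥160 | "Normal/borderline (<160) to high (≥ 160") | equal |
| Glucose | ≥126 | High ≥126 | equal |
| HDL | ≤30 | Low <40 | PCS stricter |
| Triglycerides, women | ≥120 | High ≥200 | PCS looser by 200 − 120 = 80 |
| Triglycerides, men | ≥160 | High ≥200 | PCS looser by 200 − 160 = 40 |

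The female limit lies 150 − 120 = 30 mg/dL below the top of the Normal band. In women, 120 to under 150 is Normal and PCS, and 150 to under 200 is Borderline and PCS. In men, 160 to under 200 is Borderline and PCS. No Normal value is flagged in men, because 160 is above 150.

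**Step 2. Size of the denominator effect (assumed distribution)**

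The documents give no triglyceride distribution. I assume fasting baseline values are log-normal:

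P(TG ≥ c) = 1 − Φ( ln(c / median) / log-SD )

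Worked case, median 110 mg/dL and log-SD 0.45:

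- c = 120: ln(120/110)/0.45 = 0.193, so 42.3% of women are PCS at baseline and leave the denominator.
- c = 150: ln(150/110)/0.45 = 0.689, so 24.5% are at or above the Normal bound.
- 120 to under 150: 42.3 − 24.5 = 17.8% of women are Normal in Table 2 and PCS in Table 1.
- c = 200: ln(200/110)/0.45 = 1.329, so 9.2% would leave the denominator if the limit were 200.

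Over median 100-125 and log-SD 0.45-0.50:

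| Quantity (women) | Range |
|---|---|
| Excluded at baseline, limit 120 | 34-54% |
| Excluded at baseline, limit 200 | 6-17% |
| Normal in Table 2 but PCS in Table 1 | 15-19% |

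**Step 3. Wider sensitivity range**

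Taking median 90-150, log-SD 0.45-0.55, 30-50% women and the planned 390 subjects (all but the 390 assumed), the 120/160 limits exclude 26-69% of women and 10-45% of men. Overall that is about 15-57%, or 58 to 221 of 390. A limit of 200 excludes about 4-30%, or 15 to 117 of 390.

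**Step 4. Where the effect stops**

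Take a woman who rises from 130 to 600 mg/dL. Of the eight triglyceride rows in Table 2, six count her: Normal to high, Normal to very high, Normal/borderline to high, Normal/borderline to very high, Normal to any higher band, and the increase of 50 or more. She is also in the by-visit values and changes. Section 3.9.2 puts baseline PCS values into the supporting listing as well, so she is not lost there either.

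**The case against.** The strongest reply is that a PCS flag and a shift category are different tools, and nothing in the SAP says their cut-offs must match. The PCS tables are descriptive, the study is open-label with no formal sample size calculation, and no eligibility, withdrawal or stopping rule uses these triglyceride limits. Moving the limit to 200 would also nearly duplicate an existing Table 2 row, the shift from below 200 to 200 or more.

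Part of this stands. The consequence is small and descriptive. But the near-duplication is the SAP's own pattern for total cholesterol, LDL and glucose, and PCS counts additionally take in unscheduled values. A deliberate departure for one lipid, in the looser direction, needs a reason, and none is given.

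A reader might infer four stronger things that the documents do not support:

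- **That Normal values are flagged in both sexes.** This is true of women only; in men the overlap is with Borderline.
- **That large triglyceride rises would go unseen.** The Table 2 shifts and by-visit summaries still show them.
- **That a woman who is PCS at baseline certainly cannot be counted.** For vital signs (3.9.3.1) and ECG (3.9.3.3) the SAP restricts the numerator explicitly; for laboratory values it restricts only the denominator. Exclusion from both is the natural reading, but it is an inference. Counting her in the numerator alone would make the two mismatch.
- **That many subjects are shown to be lost.** The share depends entirely on an assumed distribution.

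**Conclusion.** The inconsistency is certain from Tables 1 and 2: the female limit falls in Normal, the male limit in Borderline, and triglycerides are the only fasting lipid or glucose with a PCS limit looser than the SAP's own abnormal category. As written, the triglyceride PCS percentage mixes Normal values in women with true elevations and removes women with a Normal baseline of 120-149 from its denominator.

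The size is conditional. The ranges in the working rest on assumed log-normal baselines, and the wider inputs show how loose they are. The 34-54% also includes women whose baseline is Borderline or High; the part due to Normal baselines is the 15-19%.

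Baseline is taken after four weeks of ALKS 3831, olanzapine or placebo in the antecedent study, so a reader might also infer that exclusions will differ between treatment sequences. That is possible, but the documents contain no triglyceride data to show it.

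The effect is confined to the triglyceride PCS count and percentage. The PCS listing uses the same limits and so will hold more entries, but it loses no one. This is a **minor** point, worth correcting because the correction is cheap.

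**What to change.** In SAP Table 1, base the fasting triglyceride PCS row on Table 2's existing High boundary (200 mg/dL or more, both sexes), as the SAP already does for total cholesterol, LDL and fasting glucose. This is a matter of internal consistency, using a boundary the SAP has already chosen.

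Keep the common denominator of subjects who are not PCS at baseline. Dropping that exclusion for triglycerides alone would give one analyte a different rule from the rest of Table 1.

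If the 120/160 limits are needed for comparison with related studies, show them as a supplementary row labelled as a lower-threshold flag, with a one-line reason.

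The cost is an edit to the triglyceride entries of one table plus the matching program and mock table; no new data are needed. The downside is the loss of direct comparability with any earlier tables that used 120/160. The plans of the antecedent and follow-on studies are not among these documents, so whether such tables exist cannot be checked here. The supplementary row would cover that case.

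### No planned shift or PCS table counts subjects whose HbA1c rises from 5.7–<6.5% to 6.5% or above, the protocol's own discontinuation level

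*SAP*

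**What the plan says.** SAP 3.9.2 commits to HbA1c shifts: "Shift tables for selected metabolic parameters (glucose, total cholesterol, LDL, HDL, tryglyceride, and HbA1c) and liver function tests will be presented". It refers to Tables 2, 3 and 4 for the criteria, and HbA1c appears only in Table 3. Its three rows run from baseline <5.7% to postbaseline ≥5.7%, from <5.7% to 5.7–<6.5%, and from <5.7% to ≥6.5% ("Shift from baseline (<5.7%) to postbaseline ≥6.5" per cent).

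The fasting glucose block of the same table is wider. Besides normal to high it has "Impaired (≥100 and <126) to High (≥126" mg/dL), "Normal/Impaired (<126) to High (≥126" mg/dL) and "Increase ≥10 mg/dL".

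SAP Table 1 sets the laboratory PCS criteria. It has an entry for "Glucose, Fasting" at 126 mg/dL or above (and below 50), and one for random glucose, but none for HbA1c. The PCS denominator is defined so: "The percentages will be calculated based on the number of subjects with non-PCS baseline value and have at least 1 postbaseline assessment".

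Protocol 7.3 requires discontinuation if HbA1c is 6.5% or above at any time in the extension. Protocol 14.4 plans counts and percentages of subjects with laboratory shifts and does not itself define the categories.

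**The concern.** The subjects who start closest to 6.5% are those the HbA1c rows leave out. The trial's only objective is long-term safety and tolerability, and 6.5% is a level at which the protocol ends a subject's participation. A reader of the planned shift table would see only the crossings that began below 5.7% and could take them for the full number.

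The other laboratory trigger in Protocol 7.3, an absolute neutrophil count below 1.0 × 10³/µL, does not have this problem. Table 1 has a neutrophil PCS criterion of <1.5 × 10³/µL, which takes in every subject with a non-PCS baseline who falls below 1.0.

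**Working it through.** The plan states no figure to reproduce; the check is one of table coverage.

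**Step 1. Upward HbA1c moves against the rows of SAP Table 3.** The cut-offs 5.7% and 6.5% give three bands and three upward moves.

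| Baseline → postbaseline | Table 3 rows met | Table 1 PCS |
|---|---|---|
| <5.7% → 5.7–<6.5% | 1 and 2 | no criterion |
| <5.7% → ≥6.5% | 1 and 3 | no criterion |
| 5.7–<6.5% → ≥6.5% | none | no criterion |

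Of the two starting bands below 6.5%, one is covered for a move to ≥6.5%. Of the three HbA1c rows, none is open to a baseline of 5.7% or above.

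**Step 2. The same check on fasting glucose.** A move from 100–<126 to ≥126 mg/dL meets the impaired-to-high row and the combined row. It also meets the PCS criterion, because a baseline of 100–<126 is non-PCS and so is in the denominator.

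**Step 3. Is HbA1c an exception in the SAP?** Analytes with shift rows: Table 2 has 4 (total cholesterol, LDL, HDL, triglycerides), Table 3 has 2 (glucose, HbA1c) and Table 4 has 3 (ALT, AST, total bilirubin); 4 + 2 + 3 = 9. All but HbA1c have a Table 1 PCS criterion, so 8 of 9.

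Total cholesterol, LDL, triglycerides and glucose each use an intermediate band and each have an intermediate-to-high row and a combined row. HbA1c also uses an intermediate band but has neither. The liver tests start only from normal, but PCS criteria back them up.

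**Step 4. Worked values (illustrative, one postbaseline value each).**
- Glucose 110 → 130 mg/dL: impaired to high, yes; normal/impaired to high, yes; increase ≥10, yes (130 − 110 = 20); PCS ≥126, yes. Four entries.
- HbA1c 5.6% → 6.6%: rows 1 and 3. Two entries.
- HbA1c 6.0% → 6.6%: no row and no PCS criterion. No entry.

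**Step 5. Do other outputs supply the count?** By-visit summaries are "summary statistics (n, mean, SD, median, minimum, and maximum for continuous variables"), which do not count subjects crossing a threshold. Listings show values without tabulating them. The discontinuation reasons in Protocol 7.3 include no HbA1c category. AE tables pick up a value only if the investigator judges it clinically significant (Protocol 13.1). The glucose tables concern a different analyte.

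**Step 6. Scale.** The documents give no baseline HbA1c distribution. As an assumption only, if 10% to 40% of the planned 390 or so subjects entered at 5.7–<6.5%, then 390 × 0.10 = 39 to 390 × 0.40 = 156 subjects would lie outside every HbA1c shift row whatever their later values. That is not an estimate of how many would reach 6.5%.

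**The case against.** The strongest reply is that no safety information is lost. A subject who reaches 6.5% must be discontinued, and so enters the disposition summary (SAP 3.3) and all-cause time to discontinuation (SAP 3.8.2). The event may also be tabulated as an AE leading to discontinuation. The by-visit maximum would show that a scheduled value of 6.5% or above occurred, and the listings allow the count to be rebuilt. Each HbA1c row states its baseline band, so no printed figure would be wrong. The SAP describes these as selected parameters, and the protocol leaves the categories open.

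All of that is true, and it limits the point to a missing tabulation rather than a breach of the protocol. It does not remove the point, because none of those outputs counts the move.

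Two narrower objections have some force. Three of the four glucose entries in Step 4 record the same crossing of 126 mg/dL, so the contrast that matters is counted against not counted. And SAP 3.9.2 restricts laboratory summaries to scheduled values unless otherwise specified, so added shift rows could miss a subject whose only value of 6.5% or above came from an unscheduled test. That limit applies to every shift row in the SAP, and Protocol 7.3 asks withdrawing subjects to attend an early termination visit at which laboratory samples are due. It is no reason to leave the rows out.

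**Conclusion.** The concern holds. As the SAP stands, a move in HbA1c from 5.7–<6.5% to ≥6.5% is counted in no shift table and no PCS table, and no table specified in the SAP gives the total number moving from <6.5% to ≥6.5%. The structural size is definite: 0 of 3 HbA1c rows are open to a baseline of 5.7% or above, and HbA1c is the only one of 9 shift-table analytes without a PCS criterion. The number of subjects affected is unknown.

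The conclusion rests on the SAP text. Mock tables are in a separate document (SAP section 9) that was not available, so an extra row there cannot be ruled out. Whether 6.5% is the right clinical level is not judged here. This is a change that should be made: inexpensive, and directly relevant to a trial that reports safety.

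**What to change.** Add two HbA1c rows to SAP Table 3, following the pattern already used for glucose:

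- baseline ≥5.7% and <6.5% to postbaseline ≥6.5%
- baseline <6.5% to postbaseline ≥6.5%

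Both starting bands below 6.5% are then covered (2 of 2 instead of 1 of 2), and the second row gives the total directly. The cost is two table rows and the matching programming, with no new data and no change to any threshold or clinical rule. The existing rows keep their values. The added rows may make the reported HbA1c shifts look less favourable. A note under the table saying whether unscheduled values count would settle the remaining ambiguity.
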